- Modifications of the study protocol based upon the review of the safety data;
- Suspension or early termination of the study because of serious concerns about subjects' safety.

Confidentiality must always be maintained during all phases of DSMB review and deliberations. DSMB members must maintain strict confidentiality concerning all privileged study results provided to them.

DSMB membership reflects appropriately involved medical disciplines, also takes into account the pilot nature of our study.

No member of the DSMB has direct involvement in the conduct of the study. No member has financial, proprietary, professional, or other interests that may affect impartial, independent decision-making by the DSMB.

Meetings are set once a year and will be scheduled more frequently in case adverse effects occur more than 2x/ month of a severe AE per quarter.

The initial DSMB meeting should occur preferably before the start of the trial or as soon thereafter as possible. At this meeting the DSMB will discuss the protocol and its roll-out, mandatory triggers set for data review or analyses. Guidelines will address stopping the study for safety concerns.

Once a study is implemented, the DSMB will convene as often as necessary, but at least once annually, to examine the accumulated safety and enrollment data, review study progress, and discuss other factors (internal or external to the study) that might impact continuation of the study as designed. A DSMB meeting may be requested by DSMB members, the PI, the Duke University IRB, or study Principal Investigator at any time to

discuss safety concerns. Decisions to hold ad hoc meetings will be made by the PI and DSMB Chair. Meetings may be held by conference calls or videoconferences or as face-to-face meetings. In the event a DSMB member cannot attend a meeting, he/she may participate by conference call, in addition can provide written comments to the DSMB Chair for consideration at the meeting.

4) Necessary patient equipment/materials to generate data-points when home

Patients will be provided with a 200-page paper booklet.

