After the informed consent form (ICF) is signed, study site personnel will record via case report form (CRF) the occurrence and nature of each subject's preexisting conditions, including clinically significant signs and symptoms of the pain condition under treatment in this study. In addition, site personnel will record any new conditions as AEs. Investigators should record their assessment of the potential relatedness of each AE to galcanezumab and/or protocol procedure via CRF.

The PI will interpret and document whether or not an AE has a reasonable possibility of being related to galcanezumab, its injection, or a study procedure, taking into account the disease, co-morbid conditions, concomitant treatment or pathologies.

A “reasonable possibility” means that there is a cause and effect relationship between galcanezumab, and/or study procedure and the AE.

The PI answers “yes/no” when making this assessment.

Planned surgeries and nonsurgical interventions should not be reported as AEs unless the underlying medical condition has worsened during the course of the study.

If galcanezumab is discontinued for a given patient as a result of an AE, study site personnel must report this to the Duke IRB via CRF, clarifying if possible, the circumstances leading to discontinuations of treatment.

A severe AE (SAE) is any AE from this study that results in one of the following outcomes:

- death
- initial or prolonged inpatient hospitalization
- a life-threatening experience (that is, immediate risk of dying)
- persistent or significant disability/incapacity
- congenital anomaly/birth defect
- important medical events that may not be immediately life-threatening or result in death or hospitalization but may jeopardize the patient or may require intervention to prevent one of the other outcomes listed in the definition above. Examples of such medical events include allergic bronchospasm requiring intensive treatment in an emergency room or at home, blood dyscrasias or convulsions that do not result in inpatient hospitalization, or the development of drug dependency or drug abuse.

All AEs occurring after signing the ICF are recorded in the CRF and assessed for fulfilling criteria of SAE. SAE reports are forwarded to the Duke University IRB. For each SAE, the Duke University IRB safety commission will decide within 48h whether the case will be forwarded to Eli Lilly immediately.

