Study site personnel must alert the Duke IRB of any SAE within 24 hours of PI or any other member of the clinical team becoming aware of the event.

If alerts are issued via telephone, they are to be immediately followed with official notification on study-specific SAE forms. This 24-hour notification requirement refers to the initial SAE information and all follow-up SAE information.

Pregnancy does not meet the definition of an AE. However, to fulfill regulatory requirements any pregnancy should be reported following the SAE process to collect data on the outcome for both mother and fetus.

Investigators are not obligated to actively seek AEs or SAEs in subjects once they have completed the 90-day treatment period. However, if the investigator learns of any SAE, including a death, during the 60 day observational period, the PI must promptly notify the Duke IRB. This will also apply to an SAE after finishing the study if the PI considers the event reasonably possibly related to treatment with galcanezumab or study participation.

Suspected unexpected serious adverse reactions (SUSARs) are serious events that the investigator identifies as related to galcanezumab or procedure. United States 21 CFR 312.32 and European Union Clinical Trial Directive 2001/20/EC and the associated detailed guidances or national regulatory requirements in participating countries require the reporting of SUSARs. The Duke IRB has procedures that will be followed for the identification, recording and expedited reporting of SUSARs that are consistent with

global regulations and the associated detailed guidances.

Enrolled patients will be instructed to contact the PI and his study team as soon as possible if the patient has a complaint or problem with galcanezumab so that the situation can be assessed.

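### The SAE definition labels seriousness criteria as severe and the protocol requires no AE intensity rating, so intense but non-serious reactions are by definition not severe AEs

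*Combined protocol and SAP*

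**What the plan says.** Section 7 (Risks and Adverse Reactions) defines the term as follows: "A severe AE (SAE) is any AE from this study that results in one of the following outcomes". The list that follows covers death, hospitalization, a life-threatening experience, "persistent or significant disability/incapacity", congenital anomaly, and "important medical events that may not be immediately life-threatening or result in death or hospitalization but may jeopardize the patient" or may need intervention to prevent a listed outcome. No item is a grade of intensity.

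Elsewhere in Section 7 the word changes. The PI's follow-up duty covers AEs that are serious or otherwise medically important, and the expedited-reporting paragraph begins "Suspected unexpected serious adverse reactions (SUSARs) are serious events". Neither place defines serious separately. Section 3 (DSMB) goes back to the other word: its trigger for more frequent meetings includes "a severe AE per quarter".

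On what is recorded for each AE, Section 7 says that "site personnel will record any new conditions as AEs" and that "Investigators should record their assessment of the potential relatedness of each AE to galcanezumab and/or protocol procedure via CRF", with relatedness answered yes or no. Each AE is also checked against the SAE criteria. The Overview adds an open side-effect log kept by the patient, with no scale stated. Section 11 (Brief Statistical Analysis Plan) names no intensity grade and describes no AE table. The Overview makes the safety profile the primary criterion.

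**The concern.** Seriousness concerns the outcome of an event; severity concerns its intensity. A reaction can be intense without being serious. Here one concept has two names, and the other has neither a name nor a required field.

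Taken literally, a reaction of severe intensity that meets no listed outcome is an AE but not a *severe AE*. The final report could then say truthfully, in the protocol's own terms, that there were no severe AEs although some patients had intense reactions. In a 20-patient study the count of serious events may well be zero, so much of the safety description will rest on non-serious events, where intensity is informative. The protocol also aims for a safety profile like the one recorded in migraine patients, and that comparison is weaker if mild and severe non-serious reactions cannot be separated.

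The DSMB trigger inherits the ambiguity: a board member cannot tell from Section 3 which meaning is intended.

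**Working it through.** **Text comparison**

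- Definition (Section 7): the label is *severe*; the content is outcomes.
- Follow-up duty and SUSAR paragraph (Section 7): the word is *serious*, with no separate definition.
- Meeting trigger (Section 3): the word is *severe*.
- Required per AE (Section 7): that the new condition occurred, relatedness (yes/no), and whether the SAE criteria are met. The phrase about occurrence and nature in that section describes preexisting conditions, not AEs.
- Intensity rating: none is required in any section, including the patient log and the analysis plan.

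An intense AE that meets no outcome criterion therefore falls outside *severe AE*, and no required field shows its intensity.

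**Arithmetic**

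The plan gives no expected SAE rate and no safety precision, so there is no figure to reproduce. The one input from the documents is n = 20 (Section 11, chosen for feasibility). The event rates are assumptions, shown as ranges.

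1. *Chance of no serious event*, with s the per-patient probability of any serious event: P = (1 − s)^20.
   - s = 1%: 0.99^20 = 0.818
   - s = 2%: 0.98^20 = 0.668
   - s = 3%: 0.97^20 = 0.544
   - s = 5%: 0.95^20 = 0.358
   - s = 10%: 0.90^20 = 0.122

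   Zero is at least as likely as not up to s = 1 − 0.5^(1/20) = 3.4%.

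2. *What zero of 20 would show*: the exact one-sided 95% upper bound is 1 − 0.05^(1/20) = 13.9%.

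3. *No serious event and at least one severe non-serious reaction*. Put each patient in one of three exclusive groups: any serious event (s), no serious event but a severe-intensity AE (v), or neither. Then P = (1 − s)^20 − (1 − s − v)^20.

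| s | v | Calculation | P |
|---|---|---|---|
| 1% | 5% | 0.818 − 0.290 | 0.528 |
| 2% | 5% | 0.668 − 0.234 | 0.433 |
| 2% | 10% | 0.668 − 0.078 | 0.590 |
| 5% | 10% | 0.358 − 0.039 | 0.320 |
| 5% | 15% | 0.358 − 0.012 | 0.347 |

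4. *Sensitivity to n*. Section 11 wants 20 completers, so more than 20 patients may be exposed. With 25 (assumed), the chance of no serious event is 0.778 at s = 1% and 0.277 at s = 5%.

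**The case against.** The strongest reply is that this is a slip of one word and that the affected events are largely captured anyway. Several parts of that reply stand, and they rule out stronger readings that a reader might infer.

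- *That no intensity is recorded.* The documents do not show this. The CRF is not among them and the study database is still to be built. What can be said is that the protocol does not require an intensity rating.
- *That such reactions will be reported as not severe.* No reporting rule or table shell says so. It is a consequence of the definition, not an instruction.
- *That severe events cannot be told from mild ones.* This goes too far. Discontinuation because of an AE must be reported with its circumstances. Important medical events without hospitalization fall under the SAE definition, with bronchospasm, blood dyscrasias and convulsions among the examples. Section 4 has patients list all medications daily, so treatment taken for an AE may be visible.
- *That the information is lost for good.* Laboratory values, blood pressure, heart rate and weight are numeric and can be graded later. The problem is with subjective symptoms.
- *That SAE reporting is impaired.* The 24-hour rule is tied to SAE and its outcome list, so the wrong adjective does not change which events are sent.
- *That non-serious events are excluded from the DSMB trigger.* The sentence also mentions adverse effects more than twice a month, and DSMB members or the PI may request a meeting at any time.

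The numbers are also soft. Nothing in the documents anchors the rates. If the harm is put as no serious event together with at least two severe reactions, and the two counts are treated as independent, the probability runs from about 9% (5% serious, 5% severe) to 76% (1% serious, 20% severe).

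The claim that this is only a slip does not stand. Correcting the word repairs the label but does not supply an intensity rating for symptoms that a patient tolerates while staying on treatment. An open log with no stated scale is a poor basis for rebuilding one.

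**Conclusion.** The point holds in a limited form. The protocol calls its seriousness criteria *severe AE*, uses *serious* for the same concept elsewhere, and does not require any AE intensity rating. The study could therefore state that it had no severe AEs although intense reactions occurred. The remaining gap is mainly subjective, symptomatic reactions that neither end treatment nor count as important medical events.

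The textual finding rests on no assumption about rates; the size does. With 20 patients, no serious event is likely at a 1% per-patient rate (82%) and less likely than not at 5% (36%). At an assumed 2% serious and 10% severe non-serious rate, 59% of such trials would have no SAE and at least one severe reaction; the other combinations tabulated give 32% to 53%. These figures illustrate that the situation is plausible and do not predict what this trial will see. The change is worth making because safety is the primary criterion and the remedy is cheap.

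**What to change.** - In Section 7, rename the definition *serious AE (SAE)* and use that term consistently there and in Section 3.
- Require one investigator-rated intensity field for every AE (mild/moderate/severe, or a standard grade), independent of seriousness. If the CRF already has one, say so in the protocol.
- In Section 3, reconcile the meeting trigger with Section 7 so that it is clear whether *severe AE* there means serious, severe in intensity, or either. Which meaning to use is for the sponsor and the DSMB to decide.
- In Section 11, report the maximum intensity per patient beside the SAE count.

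The cost is one CRF field, a wording correction and one more set of table rows. The sample size does not change. The safety summary may look slightly less favourable.

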Treatment with a CGRP-neutralizing antibody, galcanezumab in this specific patient group, being seen in the PI's clinics on a regular basis, is rooted in the rationale of unmistakable presence of clinical signs of neurogenic inflammation in the painful territory, such as episodic swelling combined with redness/hyperemia, also relief by external cold application which typically patients with trigeminal or glossopharyngeal nerve pain abhor.

Primary Outcome Measures

Primary criterion is to establish an excellent safety profile that recapitulates the favorable data recorded in migraineurs. The primary pain-related objective is reduction of pain and reduced use of rescue and other anti-pain medication.

Inclusion Criteria

- G50.1 diagnosis (can encompass an add-on G50.0 and other headache G43.... codes), or G52.1 diagnosis code (with explicit mentioning of pain of glossopharyngeal origin) **AND** small fiber neuropathy diagnostic codes G63.3, G60.8, G62.8 (can encompass fibromyalgia diagnostic code M79.7)
- 18-80 years old
- not allergic to galcanezumab and other hu mAb biologics

Exclusion Criteria

- allergic to galcanezumab and other hu mAb biologics
- pregnancy

Study Design / Overview

We propose to treat patients open label for 12 weeks, with galcanezumab, supplied by Eli Lilly, as add-on to all other therapeutic measures. We propose to use a 240mg/120mg/120mg regime, with subcutaneous (self-)injections every 4 weeks.

To reflect pain experienced by patients, the primary read-out is pain level on a 0-10 visual analog scale. We will be prompting patients to record a daily summary read at the end of each day.

[figure not shown]
The second criterion is reduction of intake of anti-pain medication (rescue PRN or regular) which the patients will record.

Chronic pain, especially fibromyalgia pain combined with trigeminal or glossopharyngeal nerve pain, is a potent disruptor of circadian rhythm. We strongly believe that this is an important and hitherto under-appreciated contributor to individual disease burden. Therefore, the third criterion is assessment of circadian rhythm function. We will assess this by having the patient rate subjectively how energetic they feel during awake day-time. Wearable activity monitors will be used to address how many hours patients sleep per

24h period, with detailed focus on total duration of sleep/rest and duration of night-time sleep only.

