Before treatment, there will be a 4 week observation-only period, and another one 8 weeks post-treatment, so that the total study period will be 6 months.

We aim for 20 patients to be included in this study.

see more detailed graphics in the next section

In terms of ancillary, laboratory-based studies, we intend to draw blood before treatment and at the 45-, 75-, 105- and 135-day of treatment time-points. We will measure cytokine/chemokine/lipid pain- and inflammation markers in patients' serum, also determine microRNA in their serum, and genomic DNA polymorphisms, the latter only at baseline. Please see next section for more detail.

To establish safety of the anti-CGRP treatment in this patient cohort, blood draw at baseline and at the 45-, 75-, 105- and 135-days of treatment time-points will also include routine systemic sentinel/surveillance markers, namely comprehensive metabolic panel and complete blood count with differential, and complete urinalysis. No more than 45 ml of blood will be collected at any given visit.

In terms of additional safety parameters, we propose an open, patient-kept side-effect log, plus home-based recordings of blood pressure, heart rate and weight at a frequency of 2x/week.

We will set up a data and safety monitoring board for proper management and oversight of data handling and patient safety-related issue; see next section.

[figure not shown]
We expect to observe effective treatment, at least in a significant subgroup of patients. Effectiveness of treatment, also magnitude of any observed therapeutic effect will be correlated with the pain/inflammation proteinaceous, lipid and RNA-based biomarkers in patients' serum, also with any polymorphisms in the patients' genomic DNA.

We also expect galcanezumab treatment to show another record of safe treatment, our expectation sculpted by analysis of in-depth data from treatment of migraineurs. Yet we will remain vigilant and implement the proposed safety sentinel measures in order not to miss adverse effects. This appears prudent because trigeminal or glossopharyngeal nerve pain plus small-fiber neuropathy is a different underlying disorder than migraine, likely representing a higher prevalence in peri-menopausal female patients. We also believe it is likely that level of chronic pain suffering-associated stress will be higher in our study population than in migraineurs.

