Patients will be recruited via the PI's clinics at Duke University, the Duke Clinics that typically refer to her attention and outside clinics and providers that refer to her as well, and DEDUCE database. In case of slow recruitment patient self-help and patient advocacy associations in the facial pain arena will be informed of the ongoing study to assist with recruitment. These organizations (Facial Pain Research Foundations, Facial Pain Association) are well-known to the PI.

11) Brief Statistical Analysis Plan

Only patients who complete the study will be included in the statistical analysis.

Response to treatment will be assessed by comparing pain metrics during the 90-day treatment period vs averaged 30 day "run-in". Outcome variables will consist of selected readout parameters of "pain metrics", namely pain subjective rating on VAS (0-10) and medication co-use. Additional outcome variables include circadian rhythm-associated metrics. A daily readout for each variable will be entered into their log by each patient, or by automatic activity reads from their motion tracking device. In similar manner, we will compare pain metrics during the 90-day treatment period vs 60-day post-treatment observation.

We intend to conduct the study with an n=20 patients to successfully complete the study. This selected number appears the most feasible and practicable number. We are confident that with an n=20 we will be in a position to do justice to the objective of initial assessment of the safety of galcanezumab in the condition under study, trigeminal or glossopharyngeal pain in the context of painful small fiber neuropathy/fibromyalgia.

Following completion of the study, we will have estimates of effect sizes and corresponding 95% confidence intervals providing information on the precision of the statistical estimates of treatment effect. Power analysis will be performed based on these estimates and will provide us with guidance for sample sizes of follow-up studies that aim for demonstrating effectiveness.

The statistical analysis will be based on a linear mixed model for repeated measures. The

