time course of pain metrics reported during the treatment period will be compared with metrics during the run-in baseline. The covariance matrix describing the nature of correlations between repeated measures will be selected based on Akaike information criterion and Bayesian information criterion, as guided by our statistics software, SAS/STAT15.1. p-values <0.05 will be considered statistically significant. Effects of treatments will be investigated with the introduction of treatment as a binary covariate (we will evaluate the effects of pre- and post-treatment in two different models).

Patients' anti-pain treatment response will be correlated with blood markers for pain, inflammation and miRNA, and also for genomic markers. This approach will be pursued in order to identify candidate biomarkers that pre-dispose patients to experience an effective or non-effective treatment response. In case of recording any particular safety-related parameters, correlation of these markers to safety metrics will also be conducted. Association between molecular biomarkers and pain- and activity-related metrics will be evaluated (i) at each time point separately using a linear regression model; (ii) by modeling the association across all time points and including time covariate in the linear regression model. The ensemble of these approaches will help determine the periods when pain or activity-related metrics and molecular markers co-evolve and become highly correlated.

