Appendix

Informed Consent Form

The PI and her team are responsible for:

- ensuring that the patient/patient's legal representative understands the nature of the study, the potential risks and benefits of participating in the study, and that their participation is voluntary.
- ensuring that informed consent is given by each patient or legal representative. This includes obtaining the appropriate signatures and dates on the ICF prior to the performance of any protocol procedures and prior to the administration of galcanezumab
- answering any questions the patient/patient's legal representative may have throughout the study and sharing in a timely manner any new information that may be relevant to the patient's willingness to continue her participation in the study.
- ensuring that a copy of the ICF is provided to the patient and is kept on file.
- ensuring that the medical record includes a statement that written informed consent was obtained before the patient was enrolled in the study and the date the written consent was obtained. The authorized study team-member obtaining the informed consent must also sign the ICF.

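### Safety is the primary criterion of an uncontrolled trial, yet the plan sets no run-in reference for home vital signs and no rule separating pre-dose from on-drug adverse events

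*Combined protocol and SAP*

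**What the plan says.** The Primary Outcome Measures put safety first: "Primary criterion is to establish an excellent safety profile that recapitulates the favorable data recorded in migraineurs". The Study Design / Overview describes open-label treatment with no control arm, and sets the untreated periods: "Before treatment, there will be a 4 week observation-only period, and another one 8 weeks post-treatment".

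Section 11 (Brief Statistical Analysis Plan) assesses response by "comparing pain metrics during the 90-day treatment period vs averaged 30 day" run-in. The outcomes of that comparison are the pain rating and medication co-use, and it continues: "Additional outcome variables include circadian rhythm-associated metrics". The mixed-model paragraph names only pain: "time course of pain metrics reported during the treatment period will be compared with metrics during the run-in baseline". A second comparison sets treatment against the 60-day post-treatment period, again for pain metrics. Only completers enter the statistical analysis. The one safety analysis in section 11 is conditional: if particular safety parameters are recorded, biomarkers will be correlated with them.

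On adverse events, section 7 says "All AEs occurring after signing the ICF are recorded in the CRF". The Appendix requires consent "prior to the performance of any protocol procedures and prior to the administration of galcanezumab". Section 7 also has preexisting conditions recorded separately, counts new conditions as AEs, and asks for a yes/no relatedness judgement on each. After the 90-day treatment period, investigators need not actively seek AEs.

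The other safety data are "home-based recordings of blood pressure, heart rate and weight at a frequency of 2x/week", a patient-kept side-effect log, and blood and urine tests at baseline and at four later time-points.

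**The concern.** Without a control arm, the trial needs some background against which to read its safety data. The stated aim is to match the record in migraine, but the Study Design / Overview itself says that this is a different underlying disorder and expects more stress related to chronic pain. An outside rate is therefore a weak yardstick. The run-in offers a pre-dose background in the same patients, and section 11 already uses it for effectiveness. Nothing in the plan uses it for AEs or home vital signs.

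Two things are at stake. First, the choice between counting AEs from consent and counting them from first injection stays open until the data are seen. Second, a plan followed as written would collect repeated blood pressure, heart rate and weight readings and produce no before-after estimate from them. Those are the safety data on which 20 patients could give a reasonably precise answer.

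**Working it through.** The documents give no AE rate, SD or safety sample-size calculation, so there is no stated figure to reproduce. The check is of the text, the observation windows, and what the contrast could deliver.

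**1. Does AE recording cover the run-in?** Consent comes before any procedure (Appendix), the run-in comes before treatment (Study Design / Overview), and AEs are recorded from consent (section 7). Yes. No treatment-emergent definition or split at first injection appears in section 7 or section 11.

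**2. Pre-dose share of a pooled count.** The window of active ascertainment is run-in plus treatment.
- In days: 30 / (30 + 90) = 25%.
- In weeks: 28 / (28 + 84) = 25%.

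With background rate λ per patient-month and drug excess e, over 1 month of run-in and 3 of treatment, the share is λ / [λ + 3(λ + e)]. Rates here are assumed.
- e = 0: 25% for any λ.
- λ = 0.5, e = 0.1: 0.5 / 2.3 = 22%.
- λ = 0.1, e = 0.3: 0.1 / 1.3 = 8%.

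So 25% is the ceiling when the background is constant, the drug does not lower the AE rate and patients are followed through treatment.

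**3. Effect on the proportion of patients with an AE.** With e = 0 and Poisson events, on-treatment only is 1 − exp(−3λ) and pooled is 1 − exp(−4λ).
- λ = 0.1: 26% becomes 33%.
- λ = 0.3: 59% becomes 70%.
- λ = 0.5: 78% becomes 86%.

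**4. Precision of an AE rate ratio.** For 20 patients at an assumed 0.25, 0.5 or 1 AE per patient-month with no drug excess, the expected run-in/treatment events are 5/15, 10/30 and 20/60. The 95% CI factor is exp[1.96 × √(1/a + 1/b)], which gives 2.75, 2.05 and 1.66. At the lowest rate, a ratio of 1 has an interval of about 0.36 to 2.75. These intervals treat events as independent; clustering within patients would widen them.

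**5. Do run-in home readings exist?** The Schedule of Activities is not visible in the text available. Section 5 trains patients at the initial visit to enter readings on the daily log page. The booklet's day-180 page equals 30 + 90 + 60 days, which implies that the booklet starts with the run-in. The start of readings is therefore implied, not stated.

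**6. Precision of a blood pressure contrast.** At two readings a week, each patient has 8 in the run-in and 24 on treatment, or 20 × (8 + 24) = 640 in all. The 95% half-width for the mean change is 2.093 × √{[SD_change² + SD_reading² × (1/8 + 1/24)] / 20}. The SDs are assumed.
- SD_change 3, SD_reading 8 mmHg: 2.093 × √[(9 + 10.67)/20] = 2.1 mmHg.
- SD_change 7, SD_reading 12 mmHg: 2.093 × √[(49 + 24)/20] = 4.0 mmHg.

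**The case against.** Recording AEs from consent is sound practice, and the plan says only that they are recorded. A reader might infer that the sponsor intends one pooled count that charges pre-dose events to the drug. The documents do not support that: no pooled count is defined anywhere. What stands is that no counting rule is given.

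Section 7 also deals partly with attribution. Preexisting conditions are kept apart, and a pre-injection event could hardly be judged related to galcanezumab. That is true, but a yes/no judgement by an investigator who knows the treatment neither defines an all-cause on-drug count nor supplies a background rate.

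A reader might also take the run-in to be the only untreated period, or safety to have no baseline at all. Neither is right. The 8-week post-treatment period is untreated observation too, although AEs are not actively sought then, so it is a poor AE reference. The laboratory tests do have a pre-treatment draw; what is missing is a stated analysis of change from it.

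Finally, AE rate ratios from 20 patients are imprecise, as step 4 shows. That limits them to description. It does not weaken the case for the vital-sign contrast.

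**Conclusion.** The point holds as a gap in the analysis plan for the primary criterion. Section 11 has no before-after analysis of home vital signs or laboratory tests and no definition of an on-drug AE; its only safety analysis is the conditional biomarker correlation. Missing the AE definition alone would be close to a matter of detail. The larger loss is a within-patient safety reference that the trial's own data could supply.

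The size is conditional. A pooled AE count would carry at most 25% pre-dose events under the assumptions in step 2, and 8% to 22% in the two examples with a drug excess. The 2 to 4 mmHg precision rests on assumed SDs and on home readings starting in the run-in, which the schedule would have to confirm. The change should be made, but the gap does not invalidate the trial.

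**What to change.** 1. Add home systolic and diastolic pressure, heart rate and weight to the section 11 treatment versus run-in contrast. Report mean change with 95% CI for all dosed patients, not completers only. Report laboratory tests as change from the pre-treatment draw. Confirm in the schedule that home readings start in the run-in.
2. Tabulate AEs by onset relative to first injection, and do not count pre-injection onsets as on-drug events. Give run-in and treatment rates per patient-month as description only; any ratio interval should allow for clustering within patients.
3. Show post-treatment AEs separately, labelled as passively ascertained, and do not compare their rate with the other phases.

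The cost is SAP wording and a few tables, plus an AE onset date on the CRF if it is not already captured. No visits are added. The downside is that before-after contrasts can be affected by time trends and changing reporting habits, so the results describe and do not establish causation.
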